Date of registration in primary registry	Uploaded to clinical trials on August 29 2022
Secondary identifying numbers	Red-CAP registration number Record ID 242-3
Source(s) of monetary or material support	n/a
Primary sponsor	Center for General Practice at Aalborg University (CAM AAU)
Secondary sponsor(s)	Novo Nordisk Foundation The General Practice Foundation in Denmark
Contact for public queries	[contact]
Contact for scientific queries	[contact]
Public title	The clinical impact of POCUS use in General Practice In Danish: Den kliniske betydning af brugen af ultralyd – et forskningsprojekt fra dansk almen praksis
Scientific title	The clinical impact of POCUS use: A hybrid type 2 effectiveness-implementation trial from Danish general practice
Countries of recruitment	Denmark
Health condition(s) or problem(s) studied	The use of point-of-care ultrasonography (POCUS) in general practice
Intervention(s)	An educational intervention consisting of three teaching seminars over three months, a curriculum of 10 point-of-care ultrasound (POCUS) applications, an online learning platform providing educational support before, during and after the teaching sessions.
Key inclusion and exclusion criteria	Inclusion criteria: 1. postgraduate medical doctor with a specialization in general practice. 2. work in office-based general practice in Denmark 3. access to an ultrasound device in the practice during the study period Exclusion criteria: 1. possible conflict of interest 2. no signed informed consent to participate.
Study type	A hybrid type 2 effectiveness-implementation trial
Date of first enrolment	Expected: August 2022
Target sample size	Twenty general practitioners
Recruitment status	Not yet recruiting
Primary outcome(s)	This study aims to simultaneous assess the clinical effectiveness of the intervention and to measure the impact of the implementation strategy as co-primary aims.

3 Protocol version

Version 8 August 28th 2022

4 Funding

This study will be conducted as independent research at Center for General Practice at Aalborg University and is financially supported by The Novo Nordisk Foundation (grant number 0061821) and The General Practice Foundation in Denmark (grant number A3495).

5 Roles and responsibilities

5a Names, affiliations, and roles of protocol contributors

[name] (CAA) will be the principal investigator.

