Continuous medical education for GPs is centrally organized under the wings of the Organisation of General Practitioners in Denmark (Praktiserende Lægers Organisation PLO) that has an educational branch (PLO-e). PLO-e is the practical organizer of the ultrasound course delivered in this educational intervention. PLO-e had no influence on the scientific content or data collection in the study.

The study will be coordinated from CAM AAU and data will be collected by the research team at the training sessions and by the participating general practitioners in their clinics. All study data will be stored at a secure server at Aalborg University.

Some of the GPs participating in this study may later on be eligible to have the course fee reimbursed and receive payment for the scans (approximately DKR 262 per scan). A decision regarding this lies not with the research team, but will depend on matters relating to the general practice agreement between PLO and the Danish Regions. A decision regarding this is expected in September 2022.

10 Participants

All GPs participating in two ultrasound courses organized by PLO-e (course number 9018822 and 9017222) are eligible to participate in this study. Independent of previous use of ultrasound in general practice, participants had to meet the following criteria:

Inclusion criteria:

1. Postgraduate medical doctor with a specialization in general practice
2. Working in office-based Danish general practice
3. Access to an ultrasound device in the practice during the study period

Exclusion criteria:

1. Not willing to participate in the data collection or share data for this study
2. No signed informed consent to participate

[figure not shown]
All patients seen in general practice, that the GPs find relevant to examine with POCUS can be used in the data collection. For this study, we will not collect identifiable personal or health-related data on patients. However, we will receive aggregated data on patients' age and gender. These data are used to describe the patient population but will neither be stored with the other study data nor used in analysis with other data (see section 12).

11a Description of the intervention

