Data collection participants in course 2: August 30th 2022 to November 30th 2024.

14 Sample size

This is accompanying research and as such no formal sample size calculations are made. Our potential study population is 36 GPs, who have signed up to participate in an ultrasound course organized by PLO-e. We expect a participation rate of 66% corresponding to 21 GPs. Previous cohort studies from Danish general practice have shown that GPs' average use of POCUS corresponds to once a day. With a data collection period of 24 months for participants corresponding to 200 working days, we expect approximately 8400 POCUS registrations in this study.

15 Recruitment

Two ultrasound courses delivering the educational intervention have been included in PLO-e's course catalogue for 2022 and as such all GPs working in Danish general practice has had the opportunity to sign-up for the courses. PLO-e has handled the participant recruitment and registration based on a first-come-first-served principle as well as the financial and practical aspects of organizing and executing the courses. The two ultrasound courses have a total of 36 available spots and all 36 participants are offered the opportunity to participate in the data collection for this study. However, not all participants will be offered financial compensation for participating in the study, as a collective agreement between the Danish regions and the association of GPs only allows for those GPs with in longest distance to a radiology department to have a free course attendance and a fee for performing POCUS during the data collection.

The offer to participate in the study is made upon registration to the course and repeated at the first webinar (day 1). At the webinar participants are informed about the research project and written information about the project including a consent form is distributed to participants. The signed consent forms are collected from participants on the first training seminar (day 7).

Assignment of interventions

16a Allocation Sequence generation

n/a

16b Allocation concealment mechanism

n/a

16c Implementation

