After the educational intervention, we will perform a process evaluation by collecting and assessing a number of implementation-related outcomes. We will use predefined progression criteria for all outcomes to make an interim analyses and evaluate whether adaptions to the intervention is needed prior to the large stepped wedged cluster randomized clinical trial (SW-CRT). The steering committee will perform this evaluation.

We will consider changing the intervention and/or implementation strategy if:

Implementation strategy effects:

- (I1) Adoption: less than 80% percent of participating GPs adopt the intervention and start using POCUS in their daily practice during the educational interventions (months 1-3).
- (I2) Fidelity (adherence): less than 75% of participating GPs complete the educational elements in the intervention (pre-post tests, webinars, assignments, attendance on seminar days, logbook registrations).
- (I3) Reach (penetration): less than 90% of teachers will actively support participants by engaging in the online part of the educational interventions
- (I4) Sustainability (maintenance): less than 75% of participating GPs adopt the intervention and continue to use POCUS in their daily practice following the educational interventions (months 5-6).

Development of the implementation strategy

- (D1) Adaptability: Less than 90% of teachers or participants find that the implementation of the educational intervention meets local needs
- (D2) Acceptability: Less than 90% of teachers or participants find the implementation of the educational interventions is agreeable in terms of content and delivery
- (D3) Feasibility: Less than 90% of teachers or participants find the educational intervention to be suitable for implementation
- (D4) Compatibility (appropriateness): Less than 90% of teachers or participants perceive the implementation of the educational intervention to be in line with the organisation's values, mission, priorities
- (D5) Dose (satisfaction): Less than 90% of teachers or participants are satisfied with the amount of support and resources received as part of implementation strategy

- (D6) Complexity: More than 90% of teachers or participants perceive the implementation of the educational intervention as being difficult or complex
- (D7) Context: More than 90% of teachers or participants find that organisational political, economic or social factors influenced the implementation of the educational intervention

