- (D8) Culture: More than 90% of teachers or participants find that the setting, organisational values or norms influenced the implementation of the educational intervention
- (D9) Self-efficacy: Less than 90% of teachers or participants find that they had the capacity (e.g. knowledge and skills) to implement the educational intervention
- (D10) Cost: if costs of implementation the educational intervention exceeds the budget for the research project
- (D11) Resources: if measures of the resources and managing required for the implementation the educational intervention exceeds the budget for the research project

Feasibility of trial methods

- (F1) if we are not able to recruit 66% of the eligible participants
- (F2) if we are not able to retain 66% of participants
- (F3) if we are not able to retain 90% of teachers
- (F4) if less than 90% of teachers delivered the intervention by protocol
- (F5) if less than 90% of participants received the intervention by protocol
- (F6) if less than 90% of data from registers was obtainable and valid
- (F7) if less than 90% of data collection through GP questionnaires was obtainable and valid
- (F8) if less than 90% of data collection through GP questionnaires was obtainable and valid

17 Blinding

[figure not shown]
The researcher cleaning the data set and responsible for analyzing the primary outcome will have no knowledge of participants. He is a researcher with a physiotherapy background.

Data collection, management, and analysis

18a Data collection - Plans for assessment and collection of outcome, baseline, and other trial data

Data will be collected at different timepoints.

Figure 7. Data collection

Register data: Data regarding different POCUS examinations, number of referrals, number of consultations will be delivered by PLSP (outcomes E1-3, I1 and 4). The data are registered prospectively by GPs in the medical records during the consultations from the first teaching seminar (day 7) until 24 months after the first teaching seminar (day 829). We will receive these data retrospectively from PLSP, who will use an algorithm to collect monthly aggregated data for each participating GP.

PLSP will also deliver aggregated data on patients age and gender independent from other study data.

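### Progression criterion F1 (recruit 66% of eligible GPs) needs 24 of the 36 course GPs, but the protocol plans for 21 and registers a target of 20, so recruiting to plan would miss it

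*Protocol*

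**What the plan says.** Four places in the protocol fix the recruitment figures.

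- **Registration table (target sample size):** "Twenty general practitioners".
- **Section 10 (Participants):** "All GPs participating in two ultrasound courses organized by PLO-e (course number 9018822 and 9017222) are eligible to participate in this study". Inclusion and exclusion criteria follow, and one of the exclusions is "Not willing to participate in the data collection or share data for this study".
- **Sections 14 and 15 (Sample size, Recruitment):** "Our potential study population is 36 GPs, who have signed up to participate in an ultrasound course organized by PLO-e". Section 14 continues: "We expect a participation rate of 66% corresponding to 21 GPs". Section 15 adds that "all 36 participants are offered the opportunity to participate in the data collection for this study".
- **Section 16c (Implementation):** the list of predefined progression criteria opens with "We will consider changing the intervention and/or implementation strategy if" and, among the feasibility items, gives "F1) if we are not able to recruit 66% of the eligible participants".

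Section 12 says that feasibility will be assessed partly by relating the number recruited to the possible number of participants, and that the steering committee will evaluate the results qualitatively against the progression criteria.

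**The concern.** The same 66% appears twice, as the expected participation rate in section 14 and as the F1 threshold in section 16c, so the two sections should give the same number of GPs. They do not, because section 14 converts 66% into 21 GPs and that conversion is wrong for a pool of 36. The registered target of 20 is lower still.

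Recruitment feasibility is one of the named outcomes of this preparatory study and feeds the review held before the large stepped-wedge trial. With 20 to 23 GPs recruited, a report could say truthfully both that the registered target was reached and that the recruitment criterion was missed. Fixing criteria in advance is meant to prevent that kind of choice after the result is known.

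**Working it through.** **Inputs.** Pool of 36 GPs (sections 14 and 15; section 10 calls all of them eligible). Threshold and expected rate of 66% (sections 16c and 14). Expected number 21 (section 14). Registered target 20 (registration table). Expected registrations 8,400 (section 14).

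**1. Reproducing the plan's figure.** 0.66 × 36 = 23.76, which rounds to 24. If 66% is shorthand for two thirds, 36 × 2/3 = 24 exactly. The stated 21 is not reproduced. Truncating gives 23, not 21, and 23 would still be below 66%. In the other direction, 21/36 = 58.3% and 21/0.66 = 31.8; the protocol gives no pool of that size.

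**2. Whether 21 is an isolated slip.** 8,400/21 = 400 registrations per GP, so 21 was carried forward as the working number. (400 per GP is twice the 200 working days that section 14 mentions, at one scan a day. I take 400 as the plan's implied figure and do not pursue that wording here.)

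**3. What F1 requires on 36.**

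| GPs recruited | Share of 36 | F1 (at least 66%) | Short of 24 by |
|---|---|---|---|
| 20 (registered target) | 55.6% | missed | 4 |
| 21 (section 14) | 58.3% | missed | 3 |
| 23 | 63.9% | missed | 1 |
| 24 | 66.7% | met | 0 |

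**4. Sensitivity to the denominator.** F1 refers to eligible participants, and the criteria in section 10 could leave fewer than 36.

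| Eligible pool | 20 recruits | 21 recruits |
|---|---|---|
| 30 | 66.7%, met | 70.0%, met |
| 31 | 64.5%, missed | 67.7%, met |
| 32 | 62.5%, missed | 65.6%, missed |
| 36 | 55.6%, missed | 58.3%, missed |

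So 21 recruits meet F1 only if at most 31 GPs are eligible, and 20 only if at most 30 are.

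**5. Context: chance variation.** Assume that each of the 36 GPs joins independently with the same probability p. The chance of missing F1 is then P(X ≤ 23), with X binomial(36, p).

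| True rate p | Chance of missing F1 |
|---|---|
| 50% | 96.7% |
| 21/36 (58.3%) | 80.0% |
| 66% | 45.6% |
| 75% | 9.2% |
| 80% | 1.8% |

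**The case against.** **The fault lies in section 14, not in F1.** This is largely right. F1's wording is sound, and it inherits the conflict from the conversion of 66% into 21. But correcting section 14 alone would leave the registered target of 20 below F1, so the three places have to be settled together.

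**The eligible pool may be smaller than 36.** This also stands, as a condition. A reader might infer that a study recruiting 20 or 21 GPs is certain to miss F1. The documents do not support certainty: F1 counts eligible participants, section 10 applies criteria such as access to a device, and no screened count is given. The natural reading is still 36, since section 10 calls all the course GPs eligible and section 12 compares recruits with the possible number of participants. Because unwillingness and lack of consent are themselves exclusions, F1 could even be read circularly, with refusers dropped from the denominator. That is a reason to state the denominator.

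**Missing F1 has a mild consequence.** Correct. A reader might infer that a miss stops the programme or amounts to a finding that recruitment is infeasible. The protocol says only that changes will be considered, through a qualitative evaluation by the steering committee.

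**A threshold equal to the expected rate is badly chosen.** A reader might infer this from the 45.6% in step 5. It is not an error. The protocol sets no false-alarm rate, and prompting discussion when recruitment falls below expectation is a legitimate choice. F1 also separates clearly different rates well: it is missed 96.7% of the time at a true rate of 50% and 1.8% at 80%. The binomial model is my assumption, and section 15 says that only some GPs are offered compensation, so equal probabilities are doubtful.

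**Conclusion.** The point holds as an inconsistency between figures that the protocol itself fixes. On its stated pool of 36, F1 needs 24 GPs. The expected number is 3 short of that and the registered target 4 short, so recruiting exactly to either would miss a predefined progression criterion and prompt the steering committee to consider changes. This rests on all 36 course GPs counting as eligible.

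The size is modest: a few GPs, and a discussion rather than a stop. It is worth correcting because the same figures feed the feasibility conclusion and the expected volume of data. That the threshold equals the expected rate only bears on how a narrow miss is read: 22 or 23 recruits would be compatible with a true rate of 66%.

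**What to change.** 1. **Section 16c, F1:** state the denominator as the 36 course GPs offered participation, keep the predefined 66%, and express it as at least 24 of 36.
2. **Section 14:** replace 21 with 24 GPs, and the expected registrations with about 9,600 (24 × 400, on the plan's own implied figure per GP) in place of 8,400.
3. **Registration table:** align the target with 24, or keep 20 and state that 20 to 23 GPs is a shortfall against F1.
4. **Reporting:** give the number recruited, the denominator and the percentage, and note that a narrow miss is within chance variation of the expected rate.

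F1 should not be lowered to 20. That would loosen a predefined criterion from 66% to 55.6% when, by the dates in sections 13 and 25, recruitment is probably over. It would also still be missed 43.1% of the time at a true rate of 20/36 (P(X ≤ 19), same binomial assumption), and it would be met 30.9% of the time at a true rate of 50%, against 3.3% for the 66% rule.

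The cost is a few lines of text, dated and described as a clarification that leaves the threshold unchanged. No further GPs or data are needed.

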- (D7) Context: the extent to which the teachers and participants find that organisational political, economic or social factors influenced the implementation of the educational intervention
- (D8) Culture: the extent to which the teachers and participants find that the setting, organisational values or norms influenced the implementation of the educational intervention

- (D9) Self-efficacy: the extent to which the teachers and participants find that they had the capacity (e.g. knowledge and skills) to implement the educational intervention
- (D10) Cost: measures of the cost of implementation the educational intervention
- (D11) Resources: measures of the resources and managing required for the implementation the educational intervention

Outcomes to assess the feasibility of trial methods

- (F1) the extent to which recruitment of participants was possible
- (F2) the extent to which participants retention was possible
- (F3) the extent to which retention of teachers was possible
- (F4) the extent to which teachers delivered the intervention by protocol
- (F5) the extent to which participants received the intervention by protocol
- (F6) the extent to which data collection through registers was obtainable and valid
- (F7) the extent to which data collection through GP questionnaires was obtainable and valid
- (F8) the extent to which data collection through GP questionnaires was obtainable in a questionnaire measuring GPs' sense of burnout, stress and job satisfaction estimated 3 months after introducing POCUS in general practice.

8 Trial design

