Outcomes to assess the effectiveness of the intervention:

Following the use of POCUS in the general practice consultations the GPs will follow normal procedures for registration of activities in general practice using remuneration codes, fee-specific codes for using POCUS, and referrals in the medical record system. Prior to this study 11 fee-specific codes for 11 different POCUS examinations will be installed in the medical record system. The Primary Sector Data Provider Platform (PLSP) will develop an algorithm that allows for the following data extraction on each participating GP in a given time frame: (1) number of POCUS examinations performed, (2) number of referrals, and (3) number of consultations (outcomes E1-3). PLSP will deliver monthly aggregated data for each participating GP from baseline to 24 months after baseline. These continues data will be summarized to demonstrate variation over time.

For the registration of the clinical effect of POCUS use in the consultation (outcome E4), we will use an adapted version of a questionnaire used in a previous cohort study²⁴. The GPs will be asked to specify the following for each POCUS examination: (1) organs/structures examined with POCUS (drop down menu or free text), (2) whether POCUS use entailed a change in diagnosis (yes/no), (3) whether POCUS use entailed a change in referral (yes/no), (4) whether POCUS use entailed a change in treatment (yes/no), (5) whether POCUS use entailed a change in diagnostic certainty for the GP (yes/no), (6) whether POCUS use was helpful for the GP in terms of making a decision for patient management (5-point Likert scale), (7) whether POCUS use was helpful for the GP in terms of arriving at a diagnosis (5-point Likert scale). GP will assess the questionnaire immediately after performing POCUS during consultations in clinical practice. These categorical data will be collected for each participating GP from day 7 to day 372.

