For the registration of unwanted cases (outcome E5), we will use a questionnaire giving the GPs the possibility to explain in free text using their own words to explain (1) what was scanned, (2) circumstances surrounding the scan, (3) what happened, and (4) reflections after the scan. Data will be collected from baseline to 24 months after baseline. We will report the aggregated total number of monthly registrations for each participating GP. The free text elaborations will not be reported, but passed on to the safety committee (see section 5d). The assessment of unwanted cases for the study does not substitute the GP's registration of untoward incidents required by Danish law (<https://stps.dk/da/ansvar-og-retningslinjer/vejledning/rapporteringspligt/>).

Outcomes to assess implementation strategy effects:

For the assessment of implementation strategy effects (outcomes I1-4), we will use the register data (fee specific codes) collected by PLSP on the monthly use of POCUS for each participating GP (outcomes I1 and I4) and the activities logged (pre-post tests, webinars, assignments, attendance on seminar days, logbook registrations) in the online platform used in the educational intervention (outcomes I2-3) to estimate the frequency of use and the percentage of adherence, respectively. The continues data (outcomes I1 and I4) will be collected prospectively from day 7 to day 372, while the binary data (outcomes I2 and I3) are collected retrospectively at the end of the educational intervention including registration made in the online platform from day 1 to day 97 (at the end of the educational intervention).

Outcomes to inform further development of the implementation strategy

For outcomes related to the development of the implementation strategy (outcomes D1-D11), we will use a questionnaire distributed to participants three months after introducing POCUS in

general practice and teachers following the final teaching seminar (day 97). A reminder will follow after 2 weeks. The questionnaire will include the following questions with a 5-point Likert scale:

- (D1) Did the educational intervention meets local needs?
- (D2) Was the educational interventions agreeable in terms of content and delivery?
- (D3) Was the educational intervention suitable for implementation?
- (D4) Was the educational intervention in line with your values, mission, priorities?
- (D5) Are you satisfied with the amount of support and resources allocated to you?

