- (D6) Was the educational intervention too difficult or complex to implement?
- (D7) Did any organisational political, economic or social factors influence the implementation of the educational intervention?
- (D8) Did the setting, including organisational values or norms influence the implementation of the educational intervention?
- (D9) Did you have the capacity (e.g. knowledge and skills) to implement the educational intervention?

And the following questions with a free-text answer category:

- (D10) How must did you have to invest financially to implement the educational intervention?
- (D11) How much time and resources did you have to invest to implement the educational intervention?

Outcomes to assess the feasibility of trial methods

For the assessment of the feasibility of trial methods (outcomes F1-F8), we will evaluate the data quality by calculating the proportion of missing or incomplete registrations, recruited participants in relation to possible number of participants as well as participant retention and adherence. The steering committee will discuss the results and perform a qualitative evaluation based on predefined progression criteria (see section 16c).

Regarding the GP questionnaire (outcome F8), we will pilot test validated scales to determine GPs' perceived stress (Cohen's 10-item Perceived Stress Scale), GPs' job satisfaction (Warr-Cook-Wall Job satisfaction Scale) and GPs burnout symptoms (Maslach Burnout inventory).

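### F6 asks whether register data are valid, but its only calculated measure cannot see scans that were performed and never coded

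*Protocol*

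**What the plan says.** Section 7 defines the outcome as "F6) the extent to which data collection through registers was obtainable and valid", and section 16c sets the trigger: "F6) if less than 90% of data from registers was obtainable and valid". Neither place defines valid. Section 12 gives the method for F1-F8: "we will evaluate the data quality by calculating the proportion of missing or incomplete registrations", together with recruitment, retention and adherence. It then adds: "The steering committee will discuss the results and perform a qualitative evaluation based on predefined progression criteria".

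On the data themselves, section 12 states: "Prior to this study 11 fee-specific codes for 11 different POCUS examinations will be installed in the medical record system". It also states: "PLSP will deliver monthly aggregated data for each participating GP from baseline to 24 months after baseline". Section 18a confirms that GPs make the entries in the medical record during consultations and that the trial receives monthly aggregates. For adoption and sustainability (I1, I4), section 12 says "we will use the register data (fee specific codes) collected by PLSP on the monthly use of POCUS for each participating GP". E1 uses the same counts.

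A second record of scans exists. For E4, section 12 asks the GP to fill in a short form after each POCUS examination. Section 18a has these on paper until day 96 and online from day 97 to day 372. No section links this record to F6, and section 23 plans no auditing.

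**The concern.** F6 sets two conditions and the calculation serves one of them. Whether a monthly total arrived can be counted. Whether it contains all the scans cannot be read from the total, because an uncoded scan leaves no gap in the data. A GP who scans but never codes could supply a full run of zeros.

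Incomplete coding is plausible here, although the protocol does not predict it. The codes are an extra entry during a consultation, and the reward for making it may differ between GPs: section 15 says "not all participants will be offered financial compensation for participating in the study", with the scanning fee limited to those practising furthest from radiology. Section 9 expects the payment decision in September 2022, while section 13 starts the first seminars on 31 August and 6 September.

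At stake is mainly E1, which describes use over time and between GPs and is tested by repeated measures ANOVA (section 20a). Coding that differs between GPs would look like variation in use, and coding that changes over time would look like a trend. F6 is also the place where the register method itself is judged.

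**Working it through.** The 90% in F6 is a chosen threshold with no derivation, so there is no figure to reproduce. The check asks how far coding could fall before the stated measure reacted.

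**Inputs.** From section 14: 21 GPs and about 8,400 expected registrations. The same section gives one scan a day and 200 working days, which yields 21 × 200 = 4,200; reaching 8,400 needs 400 days. Both volumes are therefore run. From section 12: 24 monthly totals per GP.

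**Assumptions, not in the protocol.** The unit of F6 is the GP-month. Scans per GP-month are Poisson with mean m. A share c of scans is coded.

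**Formulas.**
- GP-months: 21 × 24 = 504.
- m = 8,400 / 504 = 16.7, or 4,200 / 504 = 8.3.
- Scoring A, every delivered total counts: F6 = 504 / 504 = 100% for any c.
- Scoring B, stricter, a zero month counts as missing: F6 = 1 − exp(−m × c).

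| Share coded c | Coded, of 8,400 | Scoring B, m = 16.7 | Scoring B, m = 8.3 |
|---|---|---|---|
| 90% | 7,560 | 100.0% | 99.9% |
| 75% | 6,300 | 100.0% | 99.8% |
| 50% | 4,200 | 99.98% | 98.5% |
| 30% | 2,520 | 99.3% | 91.8% |
| 20% | 1,680 | 96.4% | 81.1% |

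Under scoring B, F6 falls below 90% only when c is less than −ln(0.1) / m. That is 2.303 / 16.7 = about 14%, or 2.303 / 8.3 = about 28%. Under scoring A it never falls through under-coding.

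**Effect on I1 and I4.** The protocol sets no usage threshold, so take adoption to mean any coded scan. At m = 8.3 and c = 50%, a month without codes has probability exp(−4.17) = 1.5%. Three such months in a row, the I1 window, have probability 0.0155³, about 4 in a million. At m = 16.7 one empty month has probability about 0.02%. Users would be misread as non-users only where coding is close to nil.

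**Can the E4 forms settle validity?** Suppose a GP-month has 20 scans, 10 coded and 8 with a form. There are fewer forms than codes, so nothing is flagged, although half the scans are uncoded. The comparison is informative only when forms exceed codes. It spans days 97 to 372, which is 275 days or about 9 months: roughly 21 × 9 = 189 of the 504 GP-months.

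**The case against.** The strongest reply has four parts.

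- **The unit is not fixed.** Elsewhere the protocol uses registration for the single entry a GP makes per scan, so an uncoded scan could be called a missing registration. This stands to the extent that F6 = 100% is an illustration and not something the protocol states. But that reading needs a count of scans performed. Monthly totals do not hold one, and no other source is named for F6. An analysis plan could supply it; the protocol as written pairs a validity criterion with a measure of missingness.
- **F6 prompts judgement.** The steering committee evaluates qualitatively, and section 16c speaks only of considering changes. A reader might infer that under-coded data would be certified and no change considered. The documents do not support that. Equally, the committee is given no comparator with which to notice the problem.
- **The harm can be overstated.** A reader might infer that E1 is 10-50% too low, or that I1 and I4 are badly wrong. The first only restates an assumed coding rate of 50-90%. The second fails on the arithmetic above. Constant under-coding also leaves the proportional trend in E1 intact.
- **Timing.** The progression review follows the course and precedes a stepped-wedge trial planned for 2023/2024 (sections 6 and 16c), yet section 25 says register data were unavailable until November 2024. A validity check on them could do little for that review.

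It is also tempting to declare the register valid once codes reach, say, 90% of the E4 forms. The 20-scan example shows why not: with codes capped at the form count, the ratio is 8/8 = 100% with half the scans uncoded. The same GP makes both entries, so omissions may well go together.

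**Conclusion.** The point holds, as a minor one. F6 requires validity as well as availability, and the one calculation offered can speak only to availability of the POCUS counts. Under the GP-month reading, half-coded data would score between 98.5% and 100% against a 90% threshold, whichever of the two scan volumes and two scorings is used. That rests on an assumed coding rate and, for the stricter scoring, on a Poisson model. The logical gap needs neither.

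The consequence is mainly for interpreting E1 and for judging the register as a data source. I1 and I4 are exposed only for GPs who code almost nothing, if adoption means any coded use. The documents give no evidence that coding was in fact poor.

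**What to change.** Split F6 into two reported parts.

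1. **Obtainable:** GP-months delivered divided by GP-months expected, judged against the existing 90%.
2. **One-sided check of the POCUS counts:** for each GP and month from day 97 to 372, set coded scans beside online E4 forms, using forms for examinations that one of the 11 codes covers. Flag GP-months with more forms than codes to the steering committee. Sum max(0, forms − codes) over GP-months and report it beside E1 as a lower bound on uncoded scans.

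State in advance that no flag is not proof of validity, since E4 forms are self-reported by the same GP and may be less complete than the codes. In that case report F6 as obtainable, with completeness of coding not established. Set no pass threshold on the ratio of codes to forms.

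The cost is one tabulation of two data sets already collected per GP. The limits should be stated. The check omits months 1-3 and so the I1 window, when entries are in paper logbooks and section 11a also encourages practice scans on volunteers. It also says nothing about referrals or consultations (E2, E3). Given when the register data became available, it will mainly serve the reading of E1 and the assessment of the register method.
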